## 5.2 Exclusion Criteria

1. Patients with symptomatic central nervous system (CNS) metastases. Patients with history of prior CNS metastasis must have been treated, must be asymptomatic, and must not have any of the following at the time of enrollment:
  - a. No concurrent treatment for the CNS disease (e.g. surgery, radiation, corticosteroids  $\geq$  10 mg prednisone/day or equivalent)
  - b. No progression of CNS metastases on MRI or CT for at least 14 days after last day of prior therapy for the CNS metastases
  - c. No concurrent leptomeningeal disease or cord compression
2. Patients with any history of known or suspected autoimmune disease with the specific exceptions of vitiligo, resolved childhood atopic dermatitis, psoriasis not requiring systemic treatment (within the past 2 years), and patients with a history of Grave’s disease that are now euthyroid clinically and by laboratory testing.
3. History of prior allogeneic bone marrow, stem-cell, or solid organ transplantation.
4. Criterion for excluded prior therapies:
  - a. Treatment with any major surgical procedure, systemic anti-neoplastic therapy, or investigational therapy within the 4 weeks prior to the initiation of study drug administration.
  - b. Treatment with radiation therapy within 2 weeks prior to the initiation of study drug administration.
  - c. Treatment with systemic corticosteroids ( $\geq$  10 mg per day prednisone or equivalent) or other immune suppressive drugs within the 14 days prior to the initiation of study drug administration.

- d. Prior history of Grade 3 or greater drug-related diarrhea/colitis during treatment with checkpoint inhibitors including anti-LAG-3, anti-PD-1, anti-PD-L1, or anti-CTLA-4 antibodies.
5. Clinically significant cardiovascular disease including but not limited to:
    - a. Myocardial infarction or unstable angina within the 6 months prior to the initiation of study drug.
    - b. Stroke or transient ischemic attack within 6 months prior to the initiation of study drug.
    - c. Clinically significant cardiac arrhythmias.
    - d. Uncontrolled hypertension: systolic blood pressure (SBP) > 180 mmHg, diastolic blood pressure (DBP) > 100 mmHg.
    - e. Congestive heart failure (New York Heart Association class III-IV).
    - f. Pericarditis or clinically significant pericardial effusion.
    - g. Myocarditis.
  6. Clinically significant gastrointestinal disorders including but not limited to:
    - a. Any history of gastrointestinal perforation unless the affected area has been surgically resected no less than 3 months prior to the initiation of study drug and is deemed to no longer be at risk of perforation by the investigator.
    - b. History of clinically significant gastrointestinal bleeding within 6 months prior to the initiation of study drug.
    - c. Chronic malabsorption syndromes.
    - d. Current acute or chronic diarrhea > Grade 2 in severity.
    - e. Chronic gastrointestinal infection in the 3 months prior to the initiation of study drug administration.
    - f. History of *Clostridium difficile* colitis within 3 months prior to the initiation of study drug administration.
    - g. History of acute pancreatitis within 3 months prior to the initiation of study drug administration or any history of chronic pancreatitis.
    - h. Diverticulitis that is clinically significant in the opinion of the Investigator based on the extent or severity of known disease and/or the occurrence of clinically significant disease flares within 3 months prior to the initiation of study drug administration.
  7. Clinically significant pulmonary compromise, including but not limited to pneumonia, presence of active pneumonitis or history of non-infectious pneumonitis, or a requirement for supplemental oxygen use to maintain adequate oxygenation.

8. Evidence of active viral, bacterial, or systemic fungal infection requiring parenteral treatment within 7 days prior to the initiation of study drug. Patients requiring any systemic antiviral, antifungal, or antibacterial therapy for active infection must have completed treatment no less than one week prior to the initiation of study drug.
9. Known history of positive testing for human immunodeficiency virus or history of acquired immune deficiency syndrome.
10. Known history of hepatitis B or hepatitis C infection or known positive test for hepatitis B surface antigen, hepatitis B core antigen, or hepatitis C polymerase chain reaction.
11. Second primary invasive malignancy that has not been in remission for greater than 2 years; except non-melanoma skin cancer; cervical carcinoma in situ on biopsy; or squamous intraepithelial lesion on Pap smear; localized prostate cancer (Gleason score < 6); or resected melanoma in situ.
12. History of trauma or major surgery within 4 weeks prior to the initiation of study drug administration.
13. Any serious underlying medical or psychiatric condition that would impair the ability of the patient to receive or tolerate the planned treatment at the study site.
14. Known hypersensitivity to recombinant proteins, polysorbate 80, or any excipient contained in the drug formulation or custom vehicle ([Section 6.4](#)).
15. Vaccination with any live virus vaccine within 4 weeks prior to the initiation of study drug administration. Inactivated annual influenza vaccination is allowed.
16. Dementia or altered mental status that would preclude understanding and rendering of informed consent.
17. Prisoners or other individuals who are involuntarily detained.
18. Any investigative site personnel directly affiliated with this study.
19. Any issue that in the opinion of the investigator would contraindicate the patient's participation in the study or confound the results of the study.

### **5.3 Withdrawal of Patient from the Study**

Patients who withdraw before Cycle 1 Day 42 during the Dose Escalation Phase for a reason unrelated to drug toxicity or efficacy may be considered to have inadequate data to support efficacy assessment (see [Section 4.1.1](#)). In this case, replacement patients may be enrolled but the patients will be considered in intention to treat. These patients will be followed for safety assessments (see [Section 12.2](#)).

See [Section 4.5.1](#) for replacement criteria for those patients who were planned to have paired tumor biopsies.

Procedures for handling patients who fail to appear for study visits and criteria regarding when to consider patients lost-to-follow-up (LTFU) will be defined in the Study Procedures

Manual. A patient may be determined to be LTFU after there have been 3 documented phone contact attempts. If this fails, a certified letter should be sent to the patient. Only after these attempts have failed can a patient be determined to be LTFU.

## 5.4 Rules for Study Treatment Discontinuation

Patients who tolerate treatment may continue to receive treatment with the study drug(s) as specified in the protocol until any one of the following conditions are met:

- Patient meets any criteria for immune-related disease progression (irPD)
- Withdrawal of patient due to an AE or SAE
- Withdrawal of patient consent
- Completion of protocol-defined therapy
- Investigator discretion
- Pregnancy
- Occurrence of drug-related DLT
- Dose delay > 28 days due to drug-related AE
- Repeated administration of prohibited concomitant medications
- The Sponsor, Investigator, or Regulatory Agency terminates the study
- Death

For individual patients who meet these criteria, but who are otherwise considered to be experiencing compelling clinical benefit in the judgment of the Investigator, consideration may be given to continue treatment with the MGD007 and MGA012 combination, for up to maximum of total of 12 cycles, on a case-by-case basis, in consultation with the Sponsor.

For patients who experience drug-related DLTs that occurs prior to the initiation of MGA012, or for selected immune-related adverse events clearly related to the mechanism of action of MGA012, continued treatment of patients with either MGA012 or MGD007 monotherapy, respectively, may be considered selectively on a case-by-case basis, in consultation with the Sponsor.

If the Investigator decides that the patient should be withdrawn from the study or from dosing for any reason other than disease progression, the site must enter the information in the eCRFs within 24 hours ([Section 12.2.2](#)).

## **5.5 Guidelines for Discontinuation of Patient from Study**

Patients who are no longer on treatment but are still followed on the study can be terminated from the study for the following reasons:

- Completion of protocol-defined follow-up period.
- Uncontrolled intercurrent illness unrelated to cancer that prevents continuing study follow-up.
- Noncompliance with protocol-required evaluations.
- The patient requests to be discontinued from the study, i.e., withdrawal of consent.
- The Sponsor, investigator, or regulatory agency terminates the study.
- Death

[REDACTED]

[REDACTED]

[REDACTED]

[REDACTED]

[REDACTED]

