**Figure 11 Overall Study Treatment Schema**

Patients who experience progressive disease, as evidenced by  $\geq 20\%$  increase in the dimensions of target lesions or the occurrence of new lesions, may continue therapy at the discretion of the Investigator, pending confirmation of progressive disease at the next planned tumor assessment and satisfaction of criteria for irPD. Subsequent cycles of therapy after an initial documentation of progressive disease should be administered only to patients who have demonstrated acceptable tolerance to treatment with study drug, who remain otherwise clinically stable, and who in the assessment of the Investigator, may derive clinical benefit from the continuation of treatment with study drug.

No dose reductions of MGA012 or MGD007 are allowed during the study, except for patients being treated at doses that are subsequently found to exceed the MTDs for either schedule.

Data regarding the KRAS and MMR mutational status (MSI or MSS) will be collected; statuses for both must be formally documented for patients in the Cohort Expansion Phase. Patients will be required to have at least 1 site of measurable disease as defined by RECIST 1.1 criteria ([Appendix 5](#)). In addition, patients must have had an identified tumor tissue block (preferred) and/or tumor specimens sufficient for 20 slides that can be utilized for assay of gpA33, CD3, PD-1, and PD-L1 expression via immunohistochemical staining.

Following the last dose of study drug, all patients will be followed every 3 months for survival during a 2-year Survival Follow-up Period.

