### 4.5.2 Definition of End of Study

The end of study will occur after the last patient has met off-study criteria and the data collection process is completed (time of study database lock).

End of study for each patient is defined as follows: Patient is lost to follow-up (LTFU) ([Section 5.3](#)) or discontinues from the study due to any reason listed in [Section 5.5](#). Each patient's end of study status will be recorded in the End of Study CRF page.

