## 9.12 Post-treatment Follow-Up Visits

The post-treatment follow-up period includes the following:

- Survival follow-up: approximately a 2-year period for each patient following the last dose of any study drug.
- During this time, patients will be followed via telephone or other electronic contact at 3-month intervals for follow-up of OS.
- Response status: will be collected every 3 months on all patients who discontinued from study treatment due to reasons other than PD, if they have not initiated any other cancer-directed therapy.

Post-treatment follow-up is performed until the end of study for each patient.

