### **11.1.2 Survival Assessments**

Patients who are discontinued from study treatment will be followed for survival status every 3 months for a 2-year survival follow up period following the final dose of study drug, or until they expire, withdraw consent, or are lost to follow up (see [Section 9.12](#)).

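### Protocol Section 5.5 permits ending study participation, and with it survival contact, for two reasons that Section 11.1.2 does not recognise, so OS data can be lost avoidably

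*Protocol*

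**What the plan says.** **The duty to follow survival.** Section 11.1.2 says that patients whose treatment has stopped "will be followed for survival status every 3 months for a 2-year survival follow up period following the final dose of study drug". It then names the only grounds on which this may end sooner: "or until they expire, withdraw consent, or are lost to follow up". Section 4.1, below Figure 11, says that "all patients will be followed every 3 months for survival during a 2-year Survival Follow-up Period". Section 9.12 makes this a telephone or other electronic contact.

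**The exits.** Section 5.5 concerns patients who are off treatment but still followed. They "can be terminated from the study for the following reasons", and the list includes:
- "Uncontrolled intercurrent illness unrelated to cancer that prevents continuing study follow-up"
- "Noncompliance with protocol-required evaluations"

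Neither reason appears in Section 11.1.2.

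**The link.** Under Section 4.5.2 a patient's study ends at loss to follow-up, or when the patient "discontinues from the study due to any reason listed in" Section 5.5. Section 9.12 closes with "Post-treatment follow-up is performed until the end of study for each patient".

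**The endpoint.** Protocol Section 14.6.3 and SAP Section 5.1.2 define OS as time to death from any cause, censored when the patient was last known to be alive, whatever ended follow-up. Rates at 6, 12 and 24 months are planned (SAP Section 6.6.2.3). OS is a secondary objective in Cohort Expansion and exploratory in Dose Escalation.

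**The concern.** Two sections give different answers to one question: when may survival contact stop before two years? A site that follows Section 11.1.2 keeps calling a patient with a serious intercurrent illness. A site that uses Section 5.5 may stop, and nothing in the visible text exempts vital status.

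Two things are at stake. The first is avoidable loss of data, because a remote contact about vital status needs no visit and no evaluation. The second is bias. Kaplan-Meier estimation assumes that censored patients have the same later risk as those who remain. A patient removed because of uncontrolled illness plausibly has a higher short-term risk of death, and that death would count as an OS event if it were recorded. Censoring such patients beforehand raises the OS curve.

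**Working it through.** **1. The plan's own timeline.** Enrolment of 18 months, up to 24 months of treatment and 24 months of survival follow-up give 18 + 24 + 24 = 66 months, the total in Section 4.5. The full survival period is therefore part of the planned study. The plan states no OS power, event target or precision to reproduce.

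**2. The permitted early stops, side by side.**

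| Reason | Section 11.1.2 | Sections 5.5 and 4.5.2 |
|---|---|---|
| Death | yes | yes |
| Withdrawal of consent | yes | yes |
| Loss to follow-up | yes | yes (4.5.2) |
| Study terminated | not listed | yes |
| Intercurrent illness that prevents follow-up | not listed | yes |
| Noncompliance with evaluations | not listed | yes |

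The chain is: Section 5.5 reason → end of study for that patient (4.5.2) → post-treatment follow-up stops (9.12) → OS censored at last known alive.

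Two other places fit Section 11.1.2 better. Section 5.3 requires three documented telephone attempts and then a certified letter before a patient counts as lost; the noncompliance exit has no such step. SAP Section 6.3.1 ends duration of study at withdrawal of consent, loss to follow-up, death or last contact, and names neither extra reason.

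**3. Size, by assumption.** The documents give no rate of Section 5.5 terminations. The inputs are:
- n = 25 (Section 14.1);
- exponential OS with a median of 6.4 or 7.1 months, the active-arm medians of the two third-line trials in Section 2.2;
- k patients, a fraction f = k/25, censored at a uniform time within the month before their own death.

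The true 12-month OS is 2^(−12/6.4) = 27.3%, or 2^(−12/7.1) = 31.0%.

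If a fraction f is censored just before death, the risk set hardly changes but only 1 − f of deaths are counted. The estimated cumulative hazard is then about (1 − f) times the true one, and the estimate is about S^(1−f). For k = 3 and median 6.4: 2^(−1.875 × 0.88) = 31.9%. A simulation of 400,000 patients per scenario agrees:

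| k of 25 | 12-month OS, median 6.4: formula / simulated | Simulated median (months) | 12-month OS, median 7.1: formula / simulated | Simulated median (months) |
|---|---|---|---|---|
| 1 | 28.7% / 28.6% | 6.65 | 32.5% / 32.3% | 7.37 |
| 2 | 30.2% / 30.2% | 6.94 | 34.0% / 33.9% | 7.69 |
| 3 | 31.9% / 31.6% | 7.24 | 35.7% / 35.5% | 8.05 |
| 5 | 35.4% / 35.0% | 7.90 | 39.2% / 38.8% | 8.79 |

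A 3-month window gives slightly smaller shifts (median 6.4: 28.5%, 29.9%, 31.2%, 34.3%). With k = 3, median 6.4 and the 1-month window, 6-month OS moves from 52% to 56% and 24-month OS from 7% to 10%.

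**4. Against sampling error.** Take S = 0.27, n = 25 and no censoring, with the log(−log) interval the plan specifies. The SE of S is √(0.27 × 0.73/25) = 0.089. On the transformed scale it is 0.089/(0.27 × 1.309) = 0.251, and 1.96 × 0.251 = 0.492. The limits are exp(−1.309 × e^0.492) = 12% and exp(−1.309 × e^−0.492) = 45%. A shift of 1 to 5 points lies well inside that interval.

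**The case against.** The strongest reply is that this is a set of incomplete lists, not a clash of rules. Section 11.1.2 also omits termination of the study, which Section 5.5 includes. Section 5.5 is headed as guidelines and is permissive. Its illness reason applies only where illness prevents follow-up; if a telephone call is still possible, the reason is arguably not met, and if no contact is possible the patient is close to lost. Off treatment, few evaluations remain with which not to comply. Section 11.1.1 also has treating physicians contacted about survival for some patients. OS is descriptive, and the documents tie no decision to it.

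Much of this stands, and it rules out three readings that a reader might infer:
- **That Section 5.5 ends all follow-up.** It permits termination and does not require it, and Section 12.2.3 keeps unresolved SAEs under follow-up after a patient leaves.
- **That both groups are likely to die soon.** This is plausible for uncontrolled illness. Nothing in the documents supports it for noncompliant patients, where the case is avoidable data loss.
- **That the size follows from 0.27 × 25/(25 − k)**, giving 28%, 29% and 31% for one to three patients, with 27% being the one-year OS cited in Section 2.2 for TAS-102. That removes patients at time zero and is not a Kaplan-Meier estimate with late censoring.

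The rest does not remove the point. The protocol does not say whether the follow-up that illness must prevent is a clinic visit or a telephone call. The treating-physician contact belongs to the same post-treatment follow-up, so it ends at the patient's end of study too. Discretion leaves the censoring decision to individual judgement, and the SAP has no OS sensitivity analysis for it; the one in SAP Section 6.6.2.1 covers PFS and irPFS.

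**Conclusion.** The point holds as an inconsistency that permits avoidable loss of survival data. Sections 5.5, 4.5.2 and 9.12, read together, allow survival contact to stop for two reasons that Section 11.1.2 does not admit and that Section 4.1 does not foresee. In the illness group the resulting censoring is plausibly informative and would bias OS upward.

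The size is unknown because the number of such terminations is not given. Under the assumptions above, at a median of 6.4 months, the 12-month rate rises by about 1 to 4 points for one to three patients and by about 8 points for five. All of these assume that every affected patient is censored shortly before death, which is the unfavourable case. ORR and disease control rate are not touched, and OS is a descriptive secondary or exploratory endpoint. The change is worth making because it is simple, not because the likely distortion is large.

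**What to change.** Reconcile Sections 5.5, 4.5.2 and 9.12 with Section 11.1.2:
- State that discontinuation for intercurrent illness or noncompliance ends visits and evaluations only.
- State that vital-status contact, with the patient or the treating physician, continues until death, withdrawal of consent for survival follow-up, loss to follow-up after the Section 5.3 steps, termination of the study, or the end of the 2-year period, and use the same list in all four sections.
- In SAP Section 6.6.2.3, add a table of the number of, and reasons for, OS censorings before the end of follow-up.

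The cost is a few sentences in the protocol, one table, and a few more of the 3-monthly contacts already scheduled for all patients. Treatment, sample size and the primary analyses do not change.

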#### **6.4.4 Study Infusion Preparation**

#### **6.4.5 General Guidelines and Precautions**

Under no circumstances is the Investigator allowed to release these clinical supplies for use by another physician not named on Form FDA 1572 or to administer study drug to a patient who is not enrolled in this study. Study drug must be dispensed at an institution specified on Form FDA 1572.

##### **6.4.5.1 MGD007**

**MGD007 is administered to patients at very low doses. All doses employed in this study are described in units of micrograms/kg**

A microgram ( $\mu\text{g}$ ) is  
1 millionth ( $1/10^6$ ) of a gram (g),  
1 thousandth ( $1/10^3$ ) of a milligram (mg)

**MGD007 is a CD3-targeting therapy; therefore, it is possible that MGD007 may induce severe/fatal Cytokine Release Syndrome (CRS) when administered to humans.**

**Errors in dilution could result in severe/fatal CRS.**

**Every reasonable precaution should be exercised in the preparation, verification, and administration of the MGD007 dose. Independent verification of patient weight and of the calculated dose must be carried out and documented by a second individual.**

**Similarly, the syringe pump settings should be independently reviewed and documented by a second individual before study drug administration commences.**

**MGD007 should not be administered as an IV push or bolus.** All doses of MGD007 will be administered as an IV infusion over 120 minutes with a commercially available syringe pump. **All syringe pumps must be calibrated prior to use for the administration of MGD007.**

The calculated dose will be administered based on the patient's actual weight at Day 1. Significant ( $\geq 10\%$ ) change in body weight from baseline should prompt recalculation of dose. Patients with weight ( $>120$  kg) should be dosed based on Ideal Body Weight (IBW) calculations based on the following formula:

Estimated ideal body weight in (kg):

Males: IBW =  $50 \text{ kg} + 2.3 \text{ kg}$  for each inch over 5 feet.

Females: IBW =  $45.5 \text{ kg} + 2.3 \text{ kg}$  for each inch over 5 feet.

Refer to the Pharmacy Manual for further instructions on allowable parameters for dose rounding of MGD007.

Infusion or allergic reactions may occur with the infusion of monoclonal antibodies and other protein-based therapeutics. Precautions for anaphylaxis should be observed during MGD007 administration. Supportive measures may include, but are not limited to, epinephrine, antihistamines, corticosteroids, IV fluids, vasopressors, oxygen, bronchodilators, diphenhydramine, and acetaminophen. Resuscitation equipment and other supplies for the emergency management of an allergic/toxic reaction must be available. Please refer to [Section 7.2](#) for specific guidelines regarding the management of infusion reactions. Supportive care measures consistent with optimal patient care will be provided throughout the study according to institutional standards.

